8.5 Interim Analyses

There are two interim analyses scheduled before the start of Stage 2.

The first interim analysis will be conducted after approximately 50% of the randomized subjects have completed 24 weeks of therapy in Stage 1. This analysis will use the BMS equivalent of SDTM (Study Data Tabulation Model) data (“level 1” data) to facilitate the development of models for: population pharmacokinetics; exposure-response relationships; and, as available, viral kinetics.

A second interim analysis will be conducted after the last subject has completed 24 weeks of therapy in Stage 1. This will be an analysis of the available efficacy, safety, resistance and pharmacokinetic data.

The schedule for additional analyses will depend upon the decision to initiate the Stage 2, as well as the recruiting time frame of Arms 1 & 2 relative to the time frame for Arms 3, 4, and 5. If Stage 2 is initiated, and recruiting follows projected timelines, then it is anticipated that analyses will be conducted when:

- The last subject in Arms 3, 4, and 5 completes the Week 24 visit
- The last subject in Arms 1 and 2 completes the Week 96 visit
- The last subject in Arms 3, 4, and 5 completes the Week 96 visit

9 STUDY MANAGEMENT

9.1 Compliance

9.1.1 *Compliance with the Protocol and Protocol Revisions*

The study shall be conducted as described in this approved protocol. All revisions to the protocol must be discussed with, and be prepared by, BMS. The investigator should not implement any deviation or change to the protocol without prior review and documented approval/favorable opinion from the IRB/IEC of an amendment, except where necessary to eliminate an immediate hazard(s) to study subjects.

If a deviation or change to a protocol is implemented to eliminate an immediate hazard(s) prior to obtaining IRB/IEC approval/favorable opinion, as soon as possible the deviation or change will be submitted to:

- IRB/IEC for review and approval/favorable opinion
- BMS
- Regulatory Authority(ies), if required by local regulations

Documentation of approval signed by the chairperson or designee of the IRB(s)/IEC(s) must be sent to BMS.

If an amendment substantially alters the study design or increases the potential risk to the subject: (1) the consent form must be revised and submitted to the IRB(s)/IEC(s) for review and approval/favorable opinion; (2) the revised form must be used to obtain consent from subjects

currently enrolled in the study if they are affected by the amendment; and (3) the new form must be used to obtain consent from new subjects prior to enrollment.

If the revision is done via an administrative letter, investigators must inform their IRB(s)/IEC(s).

9.1.2 *Monitoring*

BMS representatives will review data centrally to identify potential issues to determine a schedule of on-site visits for targeted review of study records.

Representatives of BMS must be allowed to visit all study site locations periodically to assess the data quality and study integrity. On site they will review study records and directly compare them with source documents, discuss the conduct of the study with the investigator, and verify that the facilities remain acceptable. Certain CRF pages and/or electronic files may serve as the source documents:

In addition, the study may be evaluated by BMS internal auditors and government inspectors who must be allowed access to CRFs, source documents, other study files, and study facilities. BMS audit reports will be kept confidential.

The investigator must notify BMS promptly of any inspections scheduled by regulatory authorities, and promptly forward copies of inspection reports to BMS.

9.1.2.1 *Source Documentation*

The Investigator is responsible for ensuring that the source data are accurate, legible, contemporaneous, original and attributable, whether the data are hand-written on paper or entered electronically. If source data are created (first entered), modified, maintained, archived, retrieved, or transmitted electronically via computerized systems (and/or any other kind of electronic devices) as part of regulated clinical trial activities, such systems must be compliant with all applicable laws and regulations governing use of electronic records and/or electronic signatures. Such systems may include, but are not limited to, electronic medical/health records (EMRs/EHRs), adverse event tracking/reporting, protocol required assessments, and/or drug accountability records).

When paper records from such systems are used in place of electronic format to perform regulated activities, such paper records should be certified copies. A certified copy consists of a copy of original information that has been verified, as indicated by a dated signature, as an exact copy having all of the same attributes and information as the original.

9.1.3 *Investigational Site Training*

Bristol-Myers Squibb will provide quality investigational staff training prior to study initiation. Training topics will include but are not limited to: GCP, AE reporting, study details and procedure, electronic CRFs, study documentation, informed consent, and enrollment of WOCBP.

9.2 Records

9.2.1 Records Retention

The investigator must retain all study records and source documents for the maximum period required by applicable regulations and guidelines, or institution procedures, or for the period specified by BMS, whichever is longer. The investigator must contact BMS prior to destroying any records associated with the study.

BMS will notify the investigator when the study records are no longer needed.

If the investigator withdraws from the study (eg, relocation, retirement), the records shall be transferred to a mutually agreed upon designee (eg, another investigator, IRB). Notice of such transfer will be given in writing to BMS.

9.2.2 Study Drug Records

It is the responsibility of the investigator to ensure that a current disposition record of study drug (inventoried and dispensed) is maintained at the study site to include the investigational product and the non-investigational product(s). Records or logs must comply with applicable regulations and guidelines and should include:

- amount received and placed in storage area
- amount currently in storage area
- label identification number or batch number
- amount dispensed to and returned by each subject, including unique subject identifiers
- amount transferred to another area/site for dispensing or storage
- nonstudy disposition (eg, lost, wasted)
- amount destroyed at study site, if applicable
- amount returned to BMS
- retain samples for bioavailability/bioequivalence, if applicable
- dates and initials of person responsible for Investigational Product dispensing/accountability, as per the Delegation of Authority Form

BMS will provide forms to facilitate inventory control if the investigational site does not have an established system that meets these requirements.

9.2.3 Case Report Forms

An investigator is required to prepare and maintain adequate and accurate case histories designed to record all observations and other data pertinent to the investigation on each individual treated or entered as a control in the investigation. Data that are derived from source documents and reported on the CRF must be consistent with the source documents or the discrepancies must be explained. Additional clinical information may be collected and analyzed in an effort to enhance understanding of product safety. CRFs may be requested for AEs and/or laboratory abnormalities that are reported or identified during the course of the study.

For sites using the BMS electronic data capture tool, electronic CRFs will be prepared for all data collection fields except for fields specific to SAEs and pregnancy, which will be reported on the paper or electronic SAE form and Pregnancy Surveillance form, respectively. Spaces may be left blank only in those circumstances permitted by study-specific CRF completion guidelines provided by BMS.

The confidentiality of records that could identify subjects must be protected, respecting the privacy and confidentiality rules in accordance with the applicable regulatory requirement(s).

The investigator will maintain a signature sheet to document signatures and initials of all persons authorized to make entries and/or corrections on CRFs.

The completed CRF, including any paper or electronic SAE/pregnancy CRFs, must be promptly reviewed, signed, and dated by the investigator or qualified physician who is a subinvestigator and who is delegated this task on the Delegation of Authority Form. For electronic CRFs, review and approval/signature is completed electronically through the BMS electronic data capture tool. The investigator must retain a copy of the CRFs including records of the changes and corrections.

Each individual electronically signing electronic CRFs must meet BMS training requirements and must only access the BMS electronic data capture tool using the unique user account provided by BMS. User accounts are not to be shared or reassigned to other individuals.

9.3 Clinical Study Report and Publications

A Signatory Investigator must be selected to sign the clinical study report.

For this protocol, the Signatory Investigator will be selected as appropriate based on the following criteria:

- External Principal Investigator designated at protocol development
- National Coordinating Investigator
- Study Steering Committee chair or their designee
- Subject recruitment (eg, among the top quartile of enrollers)
- Involvement in trial design
- Regional representation (eg, among top quartile of enrollers from a specified region or country)
- Other criteria (as determined by the study team)

The data collected during this study are confidential and proprietary to BMS. Any publications or abstracts arising from this study require approval by BMS prior to publication or presentation and must adhere to BMS's publication requirements as set forth in the approved clinical trial agreement (CTA). All draft publications, including abstracts or detailed summaries of any proposed presentations, must be submitted to BMS at the earliest practicable time for review, but at any event not less than 30 days before submission or presentation unless otherwise set forth in the CTA. BMS shall have the right to delete any confidential or proprietary information contained in any proposed presentation or abstract and may delay publication for up to 60 days for purposes of filing a patent application.

10 GLOSSARY OF TERMS

Term	Definition
Complete Abstinence	
If one form of contraception is required, Complete Abstinence is defined as complete avoidance of heterosexual intercourse and is an acceptable form of contraception for all study drugs. Female subjects must continue to have pregnancy tests. Acceptable alternate methods of highly effective contraception must be discussed in the event that the subject chooses to forego complete abstinence.
 
If two forms of contraception is required, Complete abstinence is defined as complete avoidance of heterosexual intercourse and is an acceptable form of contraception for all study drugs. Subjects who choose complete abstinence are not required to use a second method of contraception, but female subjects must continue to have pregnancy tests. Acceptable alternate methods of highly effective contraception must be discussed in the event that the subject chooses to forego complete abstinence.
 
Expanded definition Complete abstinence as defined as complete avoidance of heterosexual intercourse is an acceptable form of contraception for all study drugs. This also means that abstinence is the preferred and usual lifestyle of the patient. This does not mean periodic abstinence (eg, calendar, ovulation, symptothermal, profession of abstinence for entry into a clinical trial, post-ovulation methods) and withdrawal, which are not acceptable methods of contraception. Subjects who choose complete abstinence are not required to use a second method of contraception, but female subjects must continue to have pregnancy tests. Acceptable alternate methods of highly effective contraception must be discussed in the event that the subject chooses to forego complete abstinence

11 LIST OF ABBREVIATIONS

Term	Definition
3TC	Lamivudine
AE	adverse event
AI	accumulation index
AIDS	Acquired Immunodeficiency Syndrome
AI_AUC	AUC Accumulation Index; ratio of AUC(TAU) at steady state to AUC(TAU) after the first dose
AI_C _{max}	C _{max} Accumulation Index; ratio of C _{max} at steady state to C _{max} after the first dose
AI_C _{tau}	C _{tau} Accumulation Index; ratio of C _{tau} at steady state to C _{tau} after the first dose
ALT	alanine aminotransferase
ARV	antiretroviral
AST	aspartate aminotransferase
ATV	atazanavir
ATV/r	atazanavir boosted with ritonavir
AUC	area under the concentration-time curve
AUC(INF)	area under the concentration-time curve from time zero extrapolated to infinite time
AUC(0-T)	area under the concentration-time curve from time zero to the time of the last quantifiable concentration
AUC(TAU)	area under the concentration-time curve in one dosing interval
A-V	atrioventricular
β-HCG	beta-human chorionic gonadotrophin
BA/BE	bioavailability/bioequivalence
BID, bid	bis in die, twice daily
BCRP	Breast cancer reactive protein
BDC	Bile duct-cannulated
BMI	body mass index
BMS	Bristol-Myers Squibb
BP	blood pressure
BVM	bevirimat

Term	Definition
c	copies
c/mL	copies per milliliter
C	Celsius
C12	concentration at 12 hours
C24	concentration at 24 hours
CA	capsid
cART	Combination antiretroviral therapy
Cavg	average concentration
Cexpected-tau	expected concentration in a dosing interval
CD	Cluster designation (CD4; CD8)
CDC	Centers for Disease Control
CFC	corrected fold change
CFR	Code of Federal Regulations
CI	confidence interval
CrCl	creatinine clearance
CLR	renal clearance
C _{max} , CMAX	maximum observed concentration
C _{min} , CMIN	trough observed concentration
CMV	cytomegalovirus
CNS	Central nervous system
CRC	Clinical Research Center
CRF	Case Report Form, paper or electronic
C _{ss,avg}	average steady-state plasma concentration
CSR	Clinical study report
C _t	Expected concentration at a certain time, usually at the end of an expected future dosing interval (eg, concentration at 24 hours, concentration at 12 hours, etc.)
C _{tau}	Concentration in a dosing interval (eg, concentration at 24 hours, concentration at 12 hours, etc.)
C _{trough}	Trough observed plasma concentration
CT	Computed tomography

Term	Definition
CTA	clinical trial agreement
CTX	Cross-linked C-telopeptide of Type 1 collagen
CYP	cytochrome p-450
D/C	discontinue
DDI	drug-drug interaction
DHHS	Department of Health and Human Services
dL	deciliter
DTG	dolutegravir
EC	Ethics committee
EC	effective concentration
ECG	electrocardiogram
eCRF	Electronic Case Report Form
EDC	Electronic Data Capture
EFV	efavirenz
eg	exempli gratia (for example)
E-R	exposure-response
ESR	Expedited Safety Report
ET	Early termination or End of Treatment
EU	European Union
FAHI	Functional Assessment of HIV Infection
FDA	Food and Drug Administration
FDC	Fixed dose combination
FSH	follicle stimulating hormone
FTC	emtricitabine
g	gram
GFR	glomerular filtration rate
GCP	Good Clinical Practice
GGT	gamma-glutamyl transferase
GFR	glomerular filtration rate
GSH	glutathione

Term	Definition
h; hr	hour
HAART	Highly active antiretroviral therapy
HBsAg	hepatitis B surface antigen
HBV	hepatitis B virus
HCG	Human chorionic gonadotropin
HCV	hepatitis C virus
HCO3-	bicarbonate
HIPAA	Health Insurance Portability and Accountability Act
HIV	Human Immunodeficiency Virus
HR	heart rate
HRT	hormone replacement therapy
HS	Human serum
HuSA	Human serum albumin
IAS	International AIDS Society
IB	Investigator brochure
IC	Inhibitory concentration
ICD	International Classification of Diseases
ICF	informed consent form
ICH	International Conference on Harmonisation
ie	id est (that is)
IEC	Independent Ethics Committee
IMP	investigational medicinal products
IND	Investigational New Drug Exemption
INI	Integrase inhibitor
IP	investigational product
IRB	Institutional Review Board
IU	International Unit
IUD	intrauterine device
IV	intravenous
IVRS	interactive voice response system

Term	Definition
GALT	Gut associated lymphoid tissue
GI	gastrointestinal
kg	kilogram
L	liter
MAD	multiple ascending dose
MC	micronized crystalline
mg	milligram
MI	Maturation inhibitor
MIC	minimum inhibitory concentration
min	minute
ITT	Modified Intent to Treat
mL	milliliter
mmHg	millimeters of mercury
msec	millisecond
MOA	mechanism of action
µg	microgram
µM	micromolar
N	number of subjects or observations
N/A	not applicable
ng	nanogram
nM	nanomolar
NIMP	non-investigational medicinal products
NNRTI	Non- nucleoside reverse transcriptase inhibitor
NOAEL	No observed adverse effect level
NOEL	No observed effect level
NRTI	nucleoside reverse transcriptase inhibitor
NSAID	nonsteroidal anti-inflammatory drug
pDILI	potential drug induced liver injury
PBMC	peripheral blood mononuclear cells
PCR	polymerase chain reaction

Term	Definition
PD	pharmacodynamics
PI	protease inhibitor
PDVF	Protocol-defined virologic criteria
PK	pharmacokinetics
PPI	proton pump inhibitor
PR	atrial depolarization to ventricular depolarization
PT	prothrombin time
PTT	partial thromboplastin time
QC	quality control
QD, qd	quaque die, once daily
QRS	interval representing the time for ventricular depolarization
QT	Duration of ventricular electrical activity
QTcF	QT corrected for heart rate using Frederica's formula
RAL	raltegravir
RBC	red blood cell
RNA	ribonucleic acid
RTV	ritonavir
SAD	single ascending dose
SDD	spray-dried dispersion
SAE	serious adverse event
SAP	statistical analysis plan
SD	standard deviation
SDTM	Study Data Tabulation Model
SOP	Standard Operating Procedures
SP1	spacer peptide 1
Subj	subject
STR	single tablet regimen
t	temperature
T	time
TDF	tenofovir

Term	Definition
TDF/FTC	Truvada (TDF 300 mg + FTC 200 mg)
TAO	Trial Access Online, the BMS implementation of an EDC capability
TAM	Thymidine analogue mutation
T-HALF	Half life
T-HALF _{eff} _AUC	Effective elimination half life that explains the degree of AUC accumulation observed
T _{max} , TMAX	time of maximum observed concentration
TR_AUC(0-T)	AUC(0-T) treatment ratio
TR_AUC(INF)	AUC(INF) treatment ratio
TR_Cmax	Cmax treatment ratio
UGT	UDP-glucuronosyltransferase
ULN	upper limit of normal
US	United States
VF	virologic failure
VK	Viral kinetics
VLP	Virus-like particles
WBC	white blood cell
WFD	Wallingford, Connecticut, USA
WHO	World Health Organization
Wk or WK	week
WOCBP	women of childbearing potential

APPENDIX 1 LISTINGS OF PROHIBITED AND PRECAUTIONARY THERAPIES

General Notes:

- Guidelines for the use of drugs with established or other potentially significant drug interactions listed in the Package Inserts of the marketed ARV agents used by subjects participating in this study (Reyataz[®], Norvir[®], Viread[®], Tivicay[®]) should be followed.
- Medications listed in the Package Inserts as contra-indicated with the other marketed ARV agents used by subjects participating in this study are not permitted.
- Any immunizations deemed appropriate by the subject's physician are permitted provided that the immunization is given > 4 weeks from any HIV-1 RNA measurement.
- A subject may not be co-enrolled in a concomitant trial unless it is approved by the Medical Monitor prior to randomization.

Prohibited Therapies

Drugs that should not be administered throughout the duration of the study:

Anticonvulsants: Carbamazepine, Phenobarbital, Phenytoin	Use with ATV may result in decreased ATV concentrations. Use of Carbamazepine may result in decreased DTG concentrations.
Oral Antifungals: Itraconazole, Posaconazole, and Voriconazole	Use with ATV can result in increased ATV concentrations
Antimycobacterials: Rifampin, Rifapentine, Rifabutin	These antimycobacterials decrease ATV plasma concentrations and may decrease BMS-955176 plasma concentrations.
St. John's wort	Use with ATV or DTG may result in loss of antiviral therapeutic effect
GI motility agent: Cisapride	Potential for serious and/or life threatening reactions such as cardiac arrhythmias
Pimozide	Potential for serious and/or life threatening reactions such as cardiac arrhythmias
Zetia (ezetimibe)	Ezetimibe is a substrate of OATP1B1 (of which BMS-955176 is an inhibitor in vitro).
Dofetilide	Use with DTG may result in the potential for increased Dofetilide plasma concentrations and the risk for serious and/or life threatening events
Alfuzosin	ATV increases Alfuzosin concentrations which can result in hypotension
Benzodiazepines: Triazolam and Midazolam	ATV can increase the concentration of these Benzodiazepines with the potential to increase sedation or respiratory depression
Ergot derivatives: Dihydroergotamine, ergotamine, ergonovine, methylergonovine	ATV can increase potential for ergot toxicity (e.g. peripheral vasospasm)

HMG-CoA Reductase Inhibitors: Lovastatin, Simvastatin, Atorvastatin, Pitavastatin, Rosuvastatin, Pravastatin	Use with ATV may result in increased levels of HMG-CoA Reductase Inhibitors and potential for serious reactions such as myopathy
Antacids, H2 receptor antagonists, Proton Pump Inhibitors, Sucralfate	Use with ATV may result in decreased plasma concentrations of ATV. Use of Antacids containing Aluminium, Magnesium, or Calcium may result in decreased levels of DTG.
Macrolides: Clarithromycin	Use with ATV may result in increased Clarithromycin levels and QTc prolongation
Buprenorphine	Use with ATV may increase levels of Buprenorphine
Quetiapine	Use with ATV may increase levels of Quetiapine
Salmeterol	Use with ATV may result in increased levels of Salmeterol
Avanafil	Use with ATV may result in increased Avanafil levels
All drugs with antiretroviral activity other than those considered study therapy	Any drugs with antiretroviral activity not considered study therapy may interfere with the assessments of the study.

Precautionary Therapies

Drugs that should be administered with caution during the study:

Hormonal Contraceptives	Hormonal Contraceptives cannot be relied upon as a highly effective method of contraception. See Protocol Section 3.3.1 , for more information on Highly Effective Methods of Contraception.
Antidepressants: Trazodone, Tricyclic Antidepressants (TCA)	Use with ATV/r may result in increased plasma concentrations of trazodone and TCA
Antimalarials: Atovaquone/Proguanil, Mefloquine	Use with ATV/r may result in decreased Atovaquone/Proguanil levels. The effect of Mefloquine on ATV/r is unknown.
Benzodiazepines: Alprazolam and Diazepam	ATV can increase the concentration of these Benzodiazepines
Calcium Channel Blockers	Use with ATV may result in increased concentrations of CCB's.
Non-topical Corticosteroids: Budesonide, Fluticasone, Prednisone, Methylprednisolone, Prednisolone, Triamcinolone	Use with ATV/r may result in increased levels of glucocorticoids and adrenal insufficiency
Dexamethasone	Use with ATV may result in reduced levels of ATV.
Colchicine	Use with ATV may result in increased Colchicine levels
Metformin	Use with DTG may result in increased levels of metformin.
A cation-containing (e.g. Magnesium) laxative	If used with DTG the laxative should be taken 2 hours before or 6 hours after taking concomitant laxatives.

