After the Stage 2 Week 24 endpoint, a Continuation Dose of BMS-955176 will be selected based on data from Stages 1 and 2, and study AI468-038 with which subjects in Stage 2, Arms 3 and 4 will transition to for the remainder of the study. The switch in Stage 2 may occur sooner, between Week 24 and Week 48, or it may be after Week 48.

The assigned backbone for each arm, ATV and DTG, or ATV/r and DTG, will remain unaltered throughout the study.

All subjects in both stages are expected to receive study treatment for 96 weeks.

Study Population:**Key Inclusion Criteria:**

- Men and non-pregnant women, at least 18 years of age (or minimum age as determined by local regulatory or as legal requirements dictate)
- Antiretroviral treatment-experienced, defined as having documented evidence of having failed 1 or 2 regimens that include 2 or 3 classes of ARV (with or without documented resistance)
- Confirmed Plasma HIV-1 RNA \geq 400 copies/mL
- CD4+ T-cell count $>$ 50 cells/mm³
- Screening genotype/phenotype indicating susceptibility to study drugs (unboosted ATV, FC $<$ 2.2; DTG; TDF)

Key Exclusion Criteria:

- Antiretroviral treatment-experienced adults who have failed $>$ 2 ARV regimens
- Resistance or partial resistance to any study drug
- Three or more of the following PI mutations, historical or documented: M36I/V, M46I/L/T, G48M/V, I54V/L/T/M/A, G73S/A/C/T, V82A/F/T/S/I, or L90M
- Any major ATV mutations, historical or documented: I50L, I84V/A, N88D/S
- Any major TDF mutation, historical or documented: K65R or T69ins
- Three or more of the following non-accessory thymidine analogue mutations (TAMs): M41L, D67N, K70R, L210W, T215Y/F, K219Q/E
- Any major mutations for raltegravir (RAL), elvitegravir (or clinically suspected INI resistance), historical or documented: T66IAK, E92Q, S147G, N155H, Q148H/K/R, Y143C/H/R, E157Q
- Chronic HBV/HCV (Positive blood screen for HBsAg; Positive blood screen for HCV Ab and HCV RNA)
- ALT or AST $>$ 3 \times ULN
- Alkaline Phosphatase $>$ 5 \times ULN
- Bilirubin \geq 1.5 \times ULN
- History of decompensated cirrhosis or active decompensated cirrhosis
- Hemoglobin $<$ 8.0 g/dL
- Platelets $<$ 50,000 cells/mm³

Study Drug: includes both Investigational [Medicinal] Products (IP/IMP) and Non-investigational [Medicinal] Products (Non-IP/Non-IMP) as listed:

Study Drug for AI468048		
Medication	Potency	IMP/Non-IMP
BMS-955176	60 mg or 120 mg ^a	IMP
Tenofovir (TDF)	300 mg	Non-IMP
Atazanavir (ATV)	200 mg and 300 mg	IMP

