1.4.3 Background Information on DTG

Dolutegravir (DTG) is a HIV-1 integrase strand transfer inhibitor indicated in combination with other ARVs for the treatment of HIV-1 infection. The most common adverse reactions of moderate to severe intensity include insomnia, fatigue, and headache. Clinicians are warned about immune reconstitution syndrome. For more information concerning DTG, please refer to the DTG/Tivicay SmPC or the DTG/Tivicay USPI.³⁰

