PHYSICAL EXAMINATION	Physical examination should complement elements obtained from the history. Acutely, the investigator may assess for signs of intravascular volume depletion (eg, orthostasis) and/or aspiration of vomitus as appropriate. Abdominal tenderness and guarding may indicate inflammation. The presence of fecal blood can indicate mucosal damage (eg, from an ulcer). Complete evaluation of dyspepsia should include an oral examination (poor dentition or pharyngeal erythema) and lungs for wheezing. ³⁷
DIAGNOSTIC EVALUATION AND MANAGEMENT	A major goal in the diagnostic evaluation of a subject with upper GI symptoms is to quickly arrive at a final diagnosis without exposing the subject to unnecessary (invasive) testing; Investigators should exercise good clinical judgment ³⁸ in this regard. A major goal of therapy is directed at correcting the underlying identifiable medical or surgical abnormalities. Consultation (eg, gastroenterologist) is recommended as clinically indicated.
Grade 1 symptoms	Subjects may be treated symptomatically. If subjects develop dyspepsia alone, generally only limited and direct diagnostic testing should be performed. ³⁷ If the subject has dyspepsia they should limit alcohol, caffeine, chocolate, tobacco, other contributing concomitant medications (eg, NSAIDs) and eating directly before bedtime. A variety of OTC medications are available to address constipation and diarrhea as indicated. Please refer to Appendix 1 for Prohibited and Precautionary Therapies.
Grade 2 symptoms ^a	Diagnostic testing may include but is not limited to the following (as clinically indicated): 
 • Serum chemistries and assessment of hemoglobin if not recently performed. • Testing for Helicobacter pylori • Serologies (eg, celiac disease) • PCR for viruses (eg, CMV) • Iron panel or Vitamin B12 level 
For subjects who develop dyspepsia or are infected with H. pylori the use of H2 antagonists, PPIs, Sucralfate, and antacids are prohibited (see Appendix 1 Prohibited Medications). If such therapy is required, discontinuation from the trial is necessary. The use of antiemetic's (eg, Prochlorperazine) can be utilized as indicated. Management should be targeted at addressing the underlying pathology.

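### The Appendix 1 row on cation-containing laxatives spaces a laxative from laxatives, so the row gives no interval between the laxative and dolutegravir (DTG)

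*Protocol*

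**What the plan says.** Appendix 1 of the protocol lists, among the therapies to be given with caution, "A cation-containing (e.g. Magnesium) laxative". The instruction beside it is "If used with DTG the laxative should be taken 2 hours before or 6 hours after taking concomitant laxatives".

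Four other places bear on the row:

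- **Appendix 1, Prohibited Therapies, antacid row.** The reason given there includes "Use of Antacids containing Aluminium, Magnesium, or Calcium may result in decreased levels of DTG".
- **Appendix 1, General Notes.** The first note says that sites should follow the "Guidelines for the use of drugs with established or other potentially significant drug interactions listed in the Package Inserts of the marketed ARV agents" used in the study. Tivicay (DTG) is one of the products it names. Section 1.4.3 also points to the label: "For more information concerning DTG, please refer to the DTG/Tivicay SmPC or the DTG/Tivicay USPI".
- **Synopsis, Study Design.** "The assigned backbone for each arm, ATV and DTG, or ATV/r and DTG, will remain unaltered throughout the study". DTG 50 mg once daily is part of all five regimens.
- **Section 6.7.1.4, Table 6.7.1.4-1, Grade 1 symptoms.** "A variety of OTC medications are available to address constipation and diarrhea as indicated. Please refer to Appendix 1 for Prohibited and Precautionary Therapies".

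**The concern.** A row that begins with use alongside DTG and then gives two time gaps should tell a site how to separate the product from DTG. This one measures the gaps from one laxative to another, and a site that reads it literally learns nothing about when DTG may be taken.

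At stake is a dosing instruction for a backbone drug shared by every arm. The appendix itself says that magnesium-containing antacids may lower DTG levels, and the row's own example of a cation is magnesium. The row also looks complete: it has a drug, a condition and two specific gaps, so a reader has little reason to look further.

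**Working it through.** No formula applies. The check is of the wording, set against the rest of the document.

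**1. Parse the sentence.**

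| Element | What the row has |
|---|---|
| Condition | use together with DTG |
| What is to be taken | the laxative |
| Gaps | 2 h before, or 6 h after |
| Measured from | concomitant laxatives |

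The number of time relations to DTG in the row is zero.

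**2. Rule out a text fault or superseded text.** The sentence is complete and grammatical, and it reads the same in the original protocol and in Revised Protocol 01. It is an operative row of the current appendix and not an entry in an amendment log. The original protocol serves only to show that the wording is not a reading error; sites are told to replace it, so it is not a second live location.

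**3. Establish the purpose.** The antacid row gives the mechanism: magnesium, aluminium or calcium products may reduce DTG levels. The laxative row names magnesium and is conditional on DTG. The purpose is therefore to separate the laxative from DTG.

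**4. Look for the interval elsewhere.** Section 4.5.1.2 has DTG taken in the morning with a meal and does not mention laxatives. Section 1.4.3 and the General Notes refer to the label without giving an interval. No other part of the protocol states one.

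**5. See what repair the wording supports.** Take DTG at 0 h.

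- *Change the subject from the laxative to DTG.* DTG is taken 2 h before the laxative (laxative at +2 h or later) or 6 h after it (laxative at −6 h or earlier). One noun changes. The object still makes sense, because Sections 3.4 and 5.3.3 use the word concomitant for medication taken alongside study drug.
- *Change the reference point to DTG instead.* The laxative is taken 2 h before DTG (−2 h or earlier) or 6 h after it (+6 h or later). This reading has to discard the phrase about concomitant laxatives altogether.

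The two repairs put the longer gap on opposite sides of the DTG dose. The wording favours the first but does not prove it, so the label has to confirm it.

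**6. See who would read the row.** The Grade 1 guidance in Section 6.7.1.4 mentions over-the-counter treatment of constipation and, in its next sentence, sends the investigator to Appendix 1. Cation-containing antacids are prohibited there, whereas the cation-containing laxative is allowed with caution, so its row needs a usable interval.

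**The case against.** The strongest reply is that the appendix already covers the matter. Its first General Note requires sites to follow the package-insert interaction guidance for DTG, and the faulty row authorises nothing contrary to that, because it sets no DTG interval at all. A reader might infer that sites are left without any rule for DTG and laxatives. The documents do not support that. The note stands, and it lowers the consequence, but it does not correct a specific-looking instruction that a site would read first.

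Exposure is also limited. Exclusion 4b in Section 3.3.2 bars current or anticipated treatment with any drug listed in Appendix 1. Read literally, this includes the precautionary list, so what remains is mainly use that was not foreseen at entry. The human gastrointestinal events reported in Sections 1.4.1.3 and 1.5 include nausea, vomiting, diarrhea and loose stools; loose stools are the opposite of a reason to give a laxative. Section 6.7.1.4 mentions constipation only in a general sentence and names no laxative. All of this stands.

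A reader might also infer that the direction of the gaps is wholly open. That goes too far: the phrase about concomitant laxatives fits once DTG is the subject and does not survive the other repair. Equally, the label is not among the documents reviewed, so the favoured repair cannot be declared correct from the protocol alone.

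**Conclusion.** The row is wrong as written. It gives a laxative-to-laxative interval and no interval between DTG and the laxative. This follows from the sentence itself and needs no outside source. That the row was meant to separate the laxative from DTG is an inference from its opening condition and the antacid row. That DTG should be the subject is the better-supported repair, subject to the label.

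The error is minor. The package-insert note already binds sites, and exclusion 4b leaves mainly unanticipated on-study use. A reader might go on to infer lowered DTG exposure, a bias between arms or a distorted response rate. The documents support none of these. They give neither the frequency of laxative use nor the size of any effect on DTG levels, DTG is in every arm, and no endpoint, analysis population, test or decision rule depends on the row.

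**What to change.** Rewrite the row with DTG as the subject, for example: *DTG should be taken 2 h before, or 6 h after, any concomitant cation-containing laxative.* Before issuing it, the sponsor should check the order of the two gaps against the DTG package insert that the General Notes already invoke. The cost is one sentence in Appendix 1, made as an administrative change. No visit, analysis or sample size is affected.
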